The majority of patients receiving anti-IL-5/IL5R inhibitors will have at least a 50% decrease in their asthma exacerbations rate in a tertiary clinic specialized in the field of severe asthma.

The level of blood and sputum eosinophils will be the main response predictor to anti-IL-5/IL5R inhibitors in a tertiary clinic specialized in the field of asthma whereas the rate of exacerbation in the year prior to the initiation of anti-IL-5/IL5R inhibitors will be the main predictor of asthma exacerbations in a non-selected population of severe asthmatics in Quebec.

Primary Objectives

1. To assess and compare the response* to treatment before and after the initiation of anti-IL-5/IL5R inhibitors in patients followed in a tertiary asthma clinic from the Province of Quebec and in a non-selected population of asthmatic subjects covered by the *Régie de l'Assurance Maladie du Québec*'s (RAMQ) public drug insurance plan or by a private drug insurance.
2. To assess the clinical response predictors to anti-IL-5/IL5R inhibitors in a cohort of severe asthmatics followed in tertiary care as well as in a non-selected population of asthmatic subjects covered by the RAMQ's public drug insurance plan *or by a private drug insurance*.

* Response to treatment will be defined by a reduction of asthma exacerbations of at least 50% *and* or a 50% or higher reduction of the OCS doses in steroid dependent patient compared to the year prior to treatment initiation.

Secondary objectives:

1. To assess the mean reduction of exacerbation in both cohorts.
2. To assess the adherence and persistence to treatment with anti-IL-5/IL5R inhibitors and ICS after treatment initiation with anti-IL-5/IL5R inhibitors..

Study populations.

A) A Tertiary asthma clinic cohort of patients 18 years and older who are followed at the outpatient asthma clinic of Sacre-Cœur Hospital and who have been treated with anti-IL-5/IL5R inhibitors between January 2016 and June 2020 and are included in the reMed database;

We will ensure that those patients had severe eosinophilic asthma inadequately controlled on high dose ICS plus additional controlled therapy and had a blood eosinophil count of 150 cells/ μ L on initiation or 300 cells/ μ L in the past 12 months and had either 2 or more significant asthma exacerbations in the past 12 months or were treated with daily oral steroids

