A retrospective pre-post anti-IL-5/IL5R inhibitors treatment cohort study using the RESP database and the hospital charts including patients with severe asthma followed at the *Hôpital du Sacré-Coeur de Montréal* (Tertiary asthma clinic cohort).

Another retrospective pre-post anti-IL-5/IL5R inhibitors treatment cohort selected from the Quebec health administrative databases and reMed database (Population-based cohort).

Cohort entry will be defined as the first prescription of anti-IL-5/IL5R inhibitors filled on or after January 1, 2016 for both cohorts.

Outcomes

Objective 1, primary outcome: Response to anti-IL-5/IL5R inhibitors, defined by a reduction of asthma exacerbations of at least 50% and a 50% or higher reduction of the OCS doses in steroid dependent patients in the year following the initiation of anti-IL-5/IL5R inhibitors compared to the year prior to treatment initiation, in the tertiary asthma clinic cohort and in the population-based cohort.

Objective 1, secondary outcomes: Exacerbation rates and OCS doses (for steroid-dependent patients) in the year preceding and following initiation of anti-IL-5/IL5R inhibitors in the tertiary asthma clinic cohort and in the population-based cohort.

Objective 2: Response to anti-IL-5/IL5R inhibitors in the tertiary asthma clinic cohort and in the population-based cohort in the year following initiation of anti-IL-5/IL5R inhibitors.

Potential Predictors

Potential clinical response predictors to anti-IL-5/IL5R inhibitors in the Tertiary asthma clinic cohort are: age, sex, atopy, body mass index, smoking habits, percent predicted FEV₁, asthma treatment prescribed, blood eosinophil count, and sputum eosinophil count at cohort entry.

Potential clinical response predictors to anti-IL-5/IL5R inhibitors in the Quebec population (Population-based cohort) are: age, sex, type of asthma treatment filled in the year before treatment initiation with anti-IL-5/IL5R inhibitors adherence to ICS in the year before and after treatment initiation with anti-IL-5/IL5R inhibitors, exacerbation rate in the year before treatment initiation with anti-IL-5/IL5R inhibitors, and socio economic status (welfare recipients).

Source of data

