The reMed database contains data on medications dispensed in community pharmacies to a sample of patients with private drug insurance. The reMed contains the HCIN, the private insurance policy number (PIPN), the type of insurance plan (co-payment, annual premium, and so on), the name, dose formulation and quantity of the medication dispensed, the date the medication was dispensed, the pharmacy & the prescriber's encoded identifier, the cost of medications, and the amount reimbursed by the insurer. The drug related variables recorded in reMed are almost identical to the variables recorded in the RAMQ Prescription Medications file. The HCIN allows the linkage of the reMed to the RAMQ and MED-ECHO databases.

Methods

After having obtained the authorization from the research ethics committee of the CIUSSS du Nord-de-l'île-de-Montréal and from the director of Professional Services, all the charts of patients who received anti-IL-5/IL5R inhibitors at the tertiary asthma clinic of *the Hôpital du Sacré-Coeur de Montréal* will be reviewed.

A response to treatment will be defined by a 50% reduction in the number of asthma exacerbations in the year following the initiation of anti-IL-5/IL5R inhibitors compared to the year preceding the initiation of the treatment or a 50% decrease in the OCS doses for steroid dependent patients.

A functional response to treatment will also be assessed in the Tertiary asthma clinic cohort. An improvement of FEV₁ of 12 % and ≥ 200 ml will be considered as clinically significant.

Asthma exacerbations will be defined by a short treatment with systemic corticosteroids (less than 14 days), visit to the emergency department or hospitalization related to asthma. If two markers of an asthma exacerbation occurred with 14 days, they will be counted as only one exacerbation. This definition will be applied in the Tertiary asthma clinic cohort and the population-based cohort.

The potential predictors of response to treatment will be collected in the Quebec registry in respiratory health (RESP) database and or the medical charts: age (continuous), sex (women/men), atopy (atopic/non atopic), body mass index (continuous), smoking habits (current or ex/never smokers)(never/ever/current), percent predicted FEV₁, asthma treatment (dose of ICS, dose of OCS if any), exacerbation rate in the year preceding treatment initiation, blood eosinophil count, and sputum eosinophil count.

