We shall require the authorization from *the Commission d'accès à l'information du Québec* to obtain the RAMQ and MED-ECHO data on healthcare utilization and medication for all subjects who have been diagnosed with asthma and who have been receiving anti-IL-5/IL5R inhibitors between January 2016 and June 2020; for example, subjects included in the tertiary asthma clinic cohort and the population-based cohort.

We will require from the RAMQ and MED-ECHO, the data on visits to the physicians, visits to the emergency departments, and hospitalizations for asthma and any other medical issues as well as the use of medication of all patients who have been diagnosed with asthma as defined by a validated operational definition(12) – 2 ambulatory visits for asthma or an hospitalization for asthma within the past 2 years a – in the year preceding the prescription of anti-IL-5/IL5R inhibitors and who have been receiving anti-IL-5/IL5R inhibitors from January 2016 to June 2020 in the Province of Quebec. We will request the data from January 2014 to June 2021.

Statistical analysis

We will estimate the proportion and confidence interval of patients' responder to anti-IL-5/IL5R inhibitors in the Tertiary asthma clinic cohort and the population-based cohort.

A logistic regression model will be used to identify the response predictors to anti-IL-5/IL5R inhibitors. Variable selection will be made with the Lasso selection procedure (13).

We will perform a Poisson regression model to compare the exacerbation rate in the year before and after the treatment initiation with anti-IL-5/IL5R inhibitors in the tertiary asthma clinic cohort and the population-based cohort. We will include all patients who received anti-IL-5/IL5R inhibitors in the analysis. The duration of follow-up will be taken into account using an offset in the Poisson regression model.

We will perform a linear regression model to compare the OCS doses in the year before and after the treatment initiation with anti-IL-5/IL5R inhibitors in the tertiary asthma clinic cohort and the population-based cohort.

Sample size and statistical power

To fulfill the primary objective

With 60 patients in the Tertiary asthma clinic cohort and an expected response rate of 50% we will have the power to identify 6 predictors (14). With 570 patients in the population-based cohort and an expected response rate of 50% we will have the power to identify more than 50 predictors (14).

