With 60 patients in the tertiary asthma clinic cohort, an expected rate of 1.48 exacerbations per year per patient (3), and an alpha error of 5%, we will have a power of 80% to show a reduction of 50% in the rate of exacerbation (1 year post- anti-IL-5/IL5R inhibitors versus 1 year pre- anti-IL-5/IL5R inhibitors). With 570 patients in the population-based cohort and the same assumptions, we will have more than 90% power to show a reduction of 50% in the rate of exacerbation (1 year post- anti-IL-5/IL5R inhibitors versus 1 year pre- anti-IL-5/IL5R inhibitors).

Limitations

Fifty eight percent of Quebecers are covered by a private drug insurance. With reMed, we will be able to obtain this data for only a small sample of patients with a private drug insurance plan.

Perspective:

Up to date, the main prognostic factor identified in subjects treated with anti-IL5 is the level of eosinophilic inflammation. However, this factor has been identified in subjects enrolled in clinical trials. It is unknown whether, smoking, co-morbidities or adherence to ICS affects the response to anti-IL-5/IL5R inhibitors. This study will be the first to answer this question in both a selected population followed in a tertiary asthma clinic and in a large population from Quebec.

Schedule of Activities

Study Procedures	Estimated Date
Ethic committee submission	November 2020
Submission to the Commission d'accès à l'information du Québec/RAMQ	December 2020
Clinical Data collection from RESP and hospital charts.	December 2020
First data analysis for clinical data And RAMQ data reception	March 2021
Submission of an abstract to the ATS	November 2021
Data Analysis	September 2021
Report and article writing	October 2021

References

1. Canada Go. Fast facts about asthma: Data compiled from the 2011 Survey on Living with Chronic Diseases in Canada

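### Without an untreated comparator, and with entry tied to the baseline count, the logistic responder model cannot tell factors that change the drug's effect from factors that only change the exacerbation rate

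*Combined protocol and SAP*

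**What the plan says.** The design is one treated group per cohort, each patient compared with his or her own past. Study design describes the clinic cohort as "A retrospective pre-post anti-IL-5/IL5R inhibitors treatment cohort study using the RESP database and the hospital charts", and the population-based cohort is built the same way. No untreated group is planned.

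The second primary objective is "To assess the clinical response predictors to anti-IL-5/IL5R inhibitors in a cohort of severe asthmatics followed in tertiary care", with the same aim in the population-based cohort. Statistical analysis gives the method: "A logistic regression model will be used to identify the response predictors to anti-IL-5/IL5R inhibitors", with Lasso selection.

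Study populations, A) requires that clinic patients "had either 2 or more significant asthma exacerbations in the past 12 months or were treated with daily oral steroids". For the population-based cohort, entry is by receipt of the drug. The reimbursement criteria contain a similar count rule, and the plan expects patients to meet them.

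Response is a fall of at least 50% from the prior year. Outcomes joins the oral corticosteroid (OCS) criterion with *and*: "defined by a reduction of asthma exacerbations of at least 50% and a 50% or higher reduction of the OCS doses in steroid dependent patients". Methods joins it with *or*: "or a 50% decrease in the OCS doses for steroid dependent patients". These must be reconciled.

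The prior-year exacerbation rate is a candidate predictor for the population-based cohort and, in the Methods list, for the clinic cohort too.

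Perspective shows how a predictor will be read: "It is unknown whether, smoking, co-morbidities or adherence to ICS affects the response to anti-IL-5/IL5R inhibitors". It adds that this study will be the first to answer that question.

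**The concern.** In a treated-only cohort, a patient's change after initiation mixes the drug effect with the change that would have happened anyway. Patients admitted because of a high count last year tend to have fewer events next year. This fall is larger for those whose underlying rate is low, because their high count owed more to chance. A factor that marks a high underlying rate therefore goes with a smaller fall, whether or not it alters the drug effect.

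Putting the prior-year count in the model does not cure this. Among patients with the same count, the factor still tells us who has the higher true rate, and so who will have more events in the following year.

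At stake is the meaning of a primary objective. A severity marker could be reported as something that weakens the response to the drug, and a marker of mild disease as something that strengthens it. Nothing in the plan separates the two readings. The only limitation it states concerns private-insurance coverage.

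**Working it through.** The plan gives no figure on this point. Its sample-size text only counts predictors (60/10 = 6; 570/10 = 57), which has no bearing on bias.

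**Inputs.** From the documents: rate 1.48 per year and a 50% reduction (Sample size), entry on two or more events (Study populations), response as a post-year count of at most half the pre-year count (Methods). Assumed: a factor that doubles the rate in both years (1.48 vs 2.96), and patient-level gamma heterogeneity with mean 1 and variance k = 0.5. The drug halves the rate in everyone, so the factor has no effect on drug response.

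**Step 1: patients with exactly two prior events.** With underlying rate m, the post-year count given two prior events is negative binomial with shape 1/k + 2 = 4 and p = (2 + m)/(2 + m + 0.5m). Response needs a post-year count of 0 or 1, with probability p⁴[1 + 4(1 − p)].

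- m = 1.48: p = 3.48/4.22 = 0.825; response 78.7%.
- m = 2.96: p = 4.96/6.44 = 0.770; response 67.5%.
- Odds ratio = (67.5/32.5)/(78.7/21.3) = 0.56.

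**Step 2: all patients with two or more prior events.** Summing over prior counts gives 78.5% and 68.4%. Odds ratio = (68.4/31.6)/(78.5/21.5) = 2.16/3.65 = 0.59.

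**Step 3: how far this depends on the assumptions.** The factor doubles the rate unless stated.

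| Setting (equal drug effect in everyone) | Odds ratio for the factor |
|---|---|
| 1.48 vs 2.96, drug halves rate, k = 0 / 0.5 / 1 | 0.39 / 0.59 / 0.68 |
| Base 3.14, rate ratio 0.85/3.14 = 0.27 (clinic data cited in the rationale), factor ×1.5 to ×2, k = 0.5 | about 0.92 (0.69 to 0.79 at two prior events) |
| 6 vs 12, rate ratio 0.3, k = 0 / 0.5 | 1.37 / 1.15 |
| First setting, k = 0.5, with 20% / 30% / 50% of candidates admitted regardless of count, zero prior counts scored as non-response | 0.92 / 1.03 / 1.16 |
| Same, zero prior counts excluded | 0.66 to 0.72 |
| Adjusted for prior-year count, all 60 combinations run | 0.15 to 0.79 |

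**Step 4: chance of a false finding in the negative direction** (nominal 2.5%; base rate 1.48, two or more prior events, k 0.5 to 0.82, rate ratio 0.4 to 0.5; Wald test, not Lasso).

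| Patients | Factor | Unadjusted | Adjusted for prior count |
|---|---|---|---|
| 570 | ×2 | 39–69% | 60–84% |
| 570 | ×1.5 | 18–36% | 27–48% |
| 60 | ×1.5 to ×2 | 2–10% | 3–14% |

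**Step 5: does a count model alone help?** With k = 0.5, P(0) = [2/(2 + m)]² and P(1) = 2[m/(2 + m)]P(0). The selected patients' mean prior count is M = [m − P(1)]/[1 − P(0) − P(1)], and their mean post count is 0.5m(2 + M)/(2 + m).

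- m = 1.48: M = (1.48 − 0.281)/0.389 = 3.08; post 1.08; rate ratio 0.351.
- m = 2.96: M = (2.96 − 0.194)/0.643 = 4.30; post 1.88; rate ratio 0.437.
- Ratio of ratios = 0.437/0.351 = 1.25, where the truth is 1.00.

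So a period-by-factor term against the same prior year is still biased (1.02 to 1.64 across the settings run). Against months 13 to 24 before entry, the reference means are m(2 + M)/(2 + m) = 2.16 and 3.76. Both rate ratios are then 0.50 and the ratio of ratios is 1.00.

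**Step 6: the limit of that remedy.** It needs stable underlying rates. If the factor group's rate was 20% lower in months 13 to 24, the ratio becomes 1/0.8 = 1.25 with no true interaction.

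**The case against.** The strongest case on the other side has four parts.

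- **Describing who reaches a 50% fall after initiation is a legitimate aim, and a logistic model serves it.** This stands. Only the Perspective wording turns the result into a statement about what alters the drug's action, so the model need not be discarded.
- **Response is relative to the patient's own baseline, so a factor that raises both years alike should largely cancel.** This is partly right. What remains comes from selecting on, or adjusting for, a noisy prior-year count and from cutting small counts at 50%. A reader might infer that every factor raising the exacerbation rate must appear as a negative predictor, so that the objective is bound to yield false results. The documents do not support that. Patients can enter on daily oral steroids with few or no exacerbations, the count rule is not itself an inclusion criterion in the population-based cohort, and the scoring of a zero prior count is not stated. Step 3 shows the unadjusted direction vanishing or reversing.
- **The effect can be made to look larger than is relevant.** With no drug effect and no heterogeneity, rates of 1 vs 2 per year give an odds ratio of 0.30. The rationale puts the reduction in exacerbations at about 50%, so that figure should not be the headline.
- **Body mass index and smoking are candidates only in the clinic cohort, where 60 patients give only a modest excess of false findings.** This stands. The material risk concerns claims-based candidates such as the Charlson score and adherence to inhaled corticosteroids (ICS).

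**Conclusion.** The concern holds in this form: the planned analysis cannot separate predictive from purely prognostic factors, and a prognostic factor can appear as a response predictor. A factor that raises the rate appears in the negative direction if the prior-year rate stays in the model. Without that adjustment, the direction depends on the event rates, the drug effect, the share entering by the oral-steroid route and the zero-count rule.

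In the central illustration the false odds ratio is 0.59 (0.56 at two prior events). With 570 patients, the chance of a false negative-direction finding is 18% to 84% over the settings run, against 2.5% nominal. With 60 patients it is 2% to 14%.

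These figures rest on an assumed heterogeneity, an assumed factor effect of ×1.5 to ×2, a factor prevalence of 50%, strict entry on two or more events and Wald tests. Neither Lasso selection nor the OCS part of response was modelled; the documents give no OCS figures.

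It does not follow that the logistic model is useless, or that any particular predictor found will be false. The interpretation in Perspective is what the design cannot carry.

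**What to change.** 1. Keep the logistic model with Lasso as a description of who meets the response definition. State how a prior-year count of zero is scored.
2. Reword Perspective, and any later report, so that its findings are *associated with change after initiation* and not factors that affect response to the drug. Add the absence of an untreated comparator, and selection on the baseline year, to Limitations.
3. Add a count model of exacerbations with period, predictor and predictor-by-period terms, taking months 13 to 24 before entry as the reference period. Base any effect-modification statement about exacerbations on that interaction only. The plan already says "We will request the data from January 2014 to June 2021", and the earliest entry is January 2016, so the months are covered for RAMQ and MED-ECHO. That sentence concerns those two sources, so confirm that reMed dispensing data reach back equally far.
4. State the limits of the added model. It assumes that underlying rates were not trending differently by predictor before initiation. It does not cover the OCS component of response. Patients without drug coverage in months 13 to 24 drop out.

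The cost is SAP wording and one further model, largely on data already requested. Fewer predictors may be claimed as modifying the drug's effect.

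### The before/after rate and OCS-dose models state no patient-level or dispersion term, and the 80% power for 60 patients does not follow from the named Poisson model

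*Combined protocol and SAP*

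**What the plan says.** Study design describes the tertiary cohort as "A retrospective pre-post anti-IL-5/IL5R inhibitors treatment cohort study using the RESP database and the hospital charts", and the population-based cohort is also pre-post. Each patient therefore supplies a before value and an after value.

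Statistical analysis gives one sentence per model: "We will perform a Poisson regression model to compare the exacerbation rate in the year before and after the treatment initiation" and "We will perform a linear regression model to compare the OCS doses in the year before and after the treatment initiation". The only refinement is "The duration of follow-up will be taken into account using an offset in the Poisson regression model". Outcomes lists these comparisons as secondary outcomes of Objective 1.

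Sample size and statistical power, under the line "To fulfill the primary objective", takes 60 tertiary-clinic patients, "an expected rate of 1.48 exacerbations per year per patient" and a 5% alpha, and concludes "we will have a power of 80% to show a reduction of 50% in the rate of exacerbation". For 570 population-cohort patients on the same assumptions it claims power above 90%. It does not give sidedness, dispersion, pre-post correlation or the power method.

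Study populations says the clinic patients must have "had either 2 or more significant asthma exacerbations in the past 12 months or were treated with daily oral steroids".

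**The concern.** A plain Poisson regression treats the two years as independent counts whose variance equals their mean. Exacerbation counts in the same patients can depart from this in two opposing ways. Variation beyond Poisson makes the plain SE too small. Positive correlation between a patient's two years makes it too large. The offset adjusts for time at risk and corrects neither. The linear model for OCS dose has the same gap: nothing says that a patient's two doses are linked.

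At stake are the intervals and p-values of the secondary before/after comparisons. A reader could not tell from the plan whether a reported rate interval is too narrow or too wide. The rate comparison is also the only treatment effect for which the plan states power, so its assumptions should be traceable.

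**Working it through.** **1. The stated power at n = 60.** Inputs from Sample size and statistical power: before rate 1.48 (taken as the pre-treatment rate), after rate 0.5 × 1.48 = 0.74, 60 patients with one year in each period, alpha 5% (two-sided assumed).

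- SE of the log rate ratio = √[(1/1.48 + 1/0.74)/60] = √(2.027/60) = 0.1838.
- Power = Φ(0.6931/0.1838 − 1.960) = Φ(1.811) = 96.5%, against 80% stated.
- Other standard two-sided methods (rate difference, square root, regression formula, exact conditional) give 96.8% to 98.5%; one-sided tests give 98.3% or more.
- Patients needed for 80%: (1.960 + 0.842)² × 2.027/0.6931² = 33.1, so 34.
- With 30 per period, the Wald power is 76.0%. Only the square-root variant (78.8%) comes within 2 points of 80%, and this layout treats the two years as different patients.
- To obtain 80% at n = 60 needs a dispersion factor φ = 60/33.1 = 1.81, or an unpaired negative binomial with k = (1.81 × 2.027 − 2.027)/2 ≈ 0.82. Neither is stated.
- At n = 570, SE = √(2.027/570) = 0.0596 and power is about 100%, so the claim of more than 90% holds.

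**2. Direction of error in the rate SE.** The only dispersion figures in the documents are the background before/after rates in Scientific rationale: 3.14 ± 2.3 and 0.85 ± 1.1. Reading ± as SD is an assumption.

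- Plain variance × n = 1/3.14 + 1/0.85 = 1.495.
- Actual variance × n = (2.3/3.14)² + (1.1/0.85)² − 2ρ(2.3/3.14)(1.1/0.85) = 2.211 − 1.896ρ.
- Equality at ρ = (2.211 − 1.495)/1.896 = 0.38.

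| Observed pre-post correlation ρ | True/plain SE | Coverage of nominal 95% |
|---|---|---|
| 0 | 1.22 | 89% |
| 0.38 | 1.00 | 95% |
| 0.5 | 0.92 | 97% |

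**3. Can the plain SE really be too large?** If counts are a Poisson mixture and entry does not depend on them, n × variance = 1/m₁ + 1/m₂ + k₁ + k₂ − 2r√(k₁k₂), where r is the correlation of the underlying rates. Since k₁ + k₂ ≥ 2√(k₁k₂), this never falls below the plain value. Entry on two or more prior-year events removes low baseline counts and can reverse that.

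Simulations used gamma heterogeneity, n = 60, underlying rate before selection 1.48 or 3.14 per year, underlying ratio 0.5 and assumed k of 0.2 to 0.8. Entry was at two or more events, with or without an assumed 30% of candidates admitted whatever their count. Coverage was judged against the ratio of means in entered patients.

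- Shared before and after heterogeneity: plain coverage about 95% to 96%.
- Independent heterogeneity: plain coverage from about 95% down to about 80%, the lowest at underlying rate 3.14.
- True/plain SE across all settings: about 0.95 to 1.5.
- Patient-clustered robust SE: coverage about 94% throughout.

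These runs are not the planned scenario. With an underlying rate of 1.48 and strict entry, entered patients average 2.8 to 3.3 prior-year events and their actual ratio is 0.22 to 0.37.

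**4. OCS dose.** With equal variances, separate rows give variance 2σ²/n where the paired value is 2σ²(1 − ρ)/n. The SE is then too large by 1/√(1 − ρ): 1.20, 1.41 and 1.83 at assumed ρ of 0.3, 0.5 and 0.7. The documents give no ρ for dose.

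**The case against.** The strongest reply is that little would change. These outcomes are secondary. When before and after rates share the same heterogeneity, the plain SE is nearly right, and the robust SE merely exchanges slight over-coverage for slight under-coverage. A material error needs weakly related before and after rates, which the documents do not establish. An estimated ratio of 0.50 at n = 60 has a plain interval of 0.35 to 0.72. Applying the background dispersion (k₁ = (2.3² − 3.14)/3.14² = 0.218, k₂ = (1.1² − 0.85)/0.85² = 0.498) widens it at most to 0.33 to 0.76, so the conclusion survives. All of this stands, and it limits the weight of the point. It does not supply the missing variance method.

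The selection argument is also softer than it looks. The entry criterion counts significant exacerbations, which are not defined. The outcome uses the definition in Methods, with its 14-day merging rule, and the two counts may differ. The criterion is imposed on the clinic cohort; for the population cohort the plan only expects compliance.

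A reader might infer four stronger claims that the documents do not support:

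- **That the rate intervals are certainly too narrow.** The sign depends on dispersion and correlation, which the plan does not give.
- **That the direction is equally open for OCS dose.** If the years enter as separate rows, positive correlation makes that interval too wide.
- **That the study is underpowered.** The named model gives more power than is claimed.
- **That a rate of 1.48 contradicts entry on two or more events.** The daily-steroid route allows it. If the two counts matched and 1.48 were the pre-treatment rate, at least 1 − 1.48/2 = 26% would have to enter that way.

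Clustered errors may also be intended; the plan does not exclude them.

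**Conclusion.** The point holds in this limited form and should be fixed. That no patient-level or dispersion term is stated is a fact of the text, and the failure of 80% at n = 60 to follow from the stated inputs is plain arithmetic (96.5%, two-sided).

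The size of the SE error is uncertain. It ranges from 0.92 to 1.22 times the plain SE on the background figures for correlations of 0.5 down to 0, and from about 0.95 to 1.5 in the simulations. The first range rests on an unlabelled ± from background literature whose patients were treated for as little as 3 months; the second rests on assumed k and on the entry count matching the outcome count.

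The power mismatch is conservative. The responder proportion, which is the primary outcome, does not use these models.

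**What to change.** - **Exacerbation rate:** fit a log-link Poisson GEE with the follow-up offset and robust SEs clustered on patient. A mixed count model with both a patient term and an overdispersion term would also serve. Pairing alone is not enough: with equal follow-up, a conditional Poisson model without robust SEs returns the plain SE.
- **OCS dose:** analyse within-patient change, by a paired or mixed model.
- **Power at n = 60:** recompute for the model actually used, stating the pre-treatment rate, dispersion, pre-post correlation and sidedness.

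The cost is about one sentence per model plus a revised power paragraph, with standard software and no new data. Rate intervals may widen or narrow, and robust SEs cover slightly under 95% at n = 60 (about 94% in the simulations).
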